3.3.3 Exploratory endpoints

Cardiac Power Output Index (CPOi) at admission to ICU post-transplant implantation and at 6h post-operation will be recorded. The difference between CPOi within individuals at admission to ICU and 6h post-operation will be calculated. Cardiac Power Output is defined as the hydraulic energy created by the ventricles per unit time. It is the product of Cardiac Output (CO), measured by Swan Ganz, and the Mean Arterial Pressure (MAP), taking into account the filling state of the individual and indexed to body size. It has been validated as a measure of pump failure in patients with cardiogenic shock. Primary graft dysfunction is effectively the failure of the cardiac allograft to generate sufficient cardiac output and therefore it has been hypothesised that low cardiac power output after transplantation will correspond to the development of PGD and the requirement for mechanical circulatory support. CPOi on admission to ICU has been shown to be correlated with donor to recipient heart mass ratio and inversely correlated to cardiopulmonary bypass time. Previous work from Birmingham has determined a rule-in, rule-out algorithm for cardiac power index as a predictor of severe PGD and early mortality.

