the individual(s) designated by the PI should input this information into the database. This should be done within 48 hours of written evidence of informed consent being filed in the site file. When a potential participant is called to hospital to receive their transplant, their ongoing consent to take part in the study must be confirmed by a designated individual in that centre. Where consent is withdrawn at this stage this should be recorded by completing the withdrawal of consent form.

Donor baseline data: The donor baseline data outlined in section 7.6.1 will be accessed from the NHSBT transplant registry. This is to avoid duplication of data collection.

Randomisation: The randomisation procedure is outlined in section 7.3 of this Protocol. The outcome of randomisation should be recorded in the CRF, by the delegated individual(s) at the recipient centre.

Organ donation: The organ donation procedure will be carried out in accordance with the UK NORS Protocol. The only change to this Protocol will be the trial treatment, as outlined in section 8 of this Protocol. The outcome of organ donation and the treatment applied should be recorded in the CRF, by the delegated individual(s) at the recipient centre.

Transplant procedure: The transplant implantation procedure will proceed according to the method chosen by the implanting surgeon. There will be no adjustments necessary as a result of taking part in this trial. Operative data will be obtained from the NHSBT Transplant registry and will not need to be recorded in the CRF.

Initial outcome data collection: The delegated individual(s) in the recipient centre should input the CPOi, echocardiogram and PGD data to the database no later than 72 hours after the transplant procedure. This should be conducted in accordance with the blinding instructions laid out in section 7.4 of this Protocol.

CPOi is a calculated variable and will be obtained by uploading the following variables to the database:

- i. Cardiac Output (L/min) measured by Swan-Ganz, using the thermodilution method and taking the average of three measurements, performed as soon as possible, and not later than 1 hour, after admission to ICU.
- ii. Cardiac Output (L/min) measured by Swan-Ganz, using the thermodilution method and taking the average of three measurements, performed 6 hours +/- 2 hours after admission to ICU

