- iii. Body surface area calculated using the DuBois and DuBois formula: Body Surface Area= 0.007184 x (Height(m) $^{0.725}$) x (Weight(kg) $^{0.425}$).
- iv. Mean Arterial Pressure (mmHg) on invasive intra-arterial blood-pressure monitoring at the time of Swan-Ganz measurements.
- v. Central Venous Pressure (mmHg) on invasive central venous pressure monitoring at the time of Swan-Ganz measurements.

As this is an exploratory outcome measure, with the intent to assess its utility based on real-world data, this will be assessed based on the above data being recorded on the intensive care electronic health record system. The measurements will be taken and recorded by the healthcare professional(s) looking after the participant. Where the outcome assessor transferring this data from the healthcare record to the trial database cannot find a measurement within the stipulated timeframe, this will be treated as missing data.

PGD will be determined based on the ISHLT consensus statement 2014 (2) and graded accordingly. PGD is defined as occurring within 24 hours, therefore all measurements included below must be taken within the first 24 hours after admission to ICU post-transplant procedure. Its definition requires the following variables to be recorded on the database:

F-CUSToS Protocol

Version Number 2.0; Dated 30 January 2025

- Ejection fraction on echocardiogram; where multiple measurements are taken the lowest estimate of ejection fraction recorded will be inputted to the database.
- ii. Haemodynamic variables taken at the time of a Swan Ganz measurement*:
 - (i) Central Venous Pressure (mmHg)
 - (ii) Pulmonary capillary wedge pressure (mmHg)
 - (iii)Cardiac Output (L/min)
 - (iv) Cardiac Index (L/min/m2)
 - (v) Mean Arterial Pressure (mmHg)
 - (vi)Transpulmonary gradient (mmHg)
 - (vii) Pulmonary artery systolic pressure (mmHg)
- iii. Vasoactive Inotrope Score (VIS), where VIS = dopamine [μ g kg⁻¹ min⁻¹] + dobutamine [μ g kg⁻¹min⁻¹] + 100×adrenaline [μ g kg⁻¹ min⁻¹] + 50×levosimendan [μ g kg⁻¹ min⁻¹] + 10×milrinone [μ g kg⁻¹ min⁻¹] + 10 000×vasopressin [units kg⁻¹ min⁻¹] + 100×noradrenaline dose [μ g kg⁻¹ min⁻¹].
- iv. Presence/absence of an intra-aortic balloon pump (IABP).
- v. Presence/absence of mechanical circulatory support (ECMO/LVAD/RVAD/BiVAD).

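### CPOi is meant to measure graft power, but section 7.7 does not record whether a circulatory device was running at either reading

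*Protocol*

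**What the plan says.** Section 3.3.3 states what the measure is for: "Cardiac Power Output is defined as the hydraulic energy created by the ventricles per unit time". It computes power from cardiac output and mean arterial pressure (MAP), allowing for filling and body size, and reports the hypothesis that "low cardiac power output after transplantation will correspond to the development of PGD and the requirement for mechanical circulatory support".

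Section 7.7 lists the inputs. The flow is "Cardiac Output (L/min) measured by Swan-Ganz, using the thermodilution method and taking the average of three measurements", first "performed as soon as possible, and not later than 1 hour, after admission to ICU" and again "performed 6 hours +/- 2 hours after admission to ICU". The pressure is "Mean Arterial Pressure (mmHg) on invasive intra-arterial blood-pressure monitoring at the time of Swan-Ganz measurements", with central venous pressure (CVP) taken at the same time. The values are read from the ICU electronic record. The one handling rule specific to CPOi is that where the assessor "cannot find a measurement within the stipulated timeframe, this will be treated as missing data".

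Device status appears later in section 7.7, in the separate list for grading PGD. There the balloon pump (IABP) and ECMO/LVAD/RVAD/BiVAD are each present or absent over the first 24 hours after ICU admission. No start or stop time is requested.

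CPOi is then used in three ways:
- Section 3.2, hypothesis 2, expects the solutions to differ on it in the first 6 hours.
- The table in section 3.3.4 compares it by PGD status and by solution, including change over time.
- Section 10.5 regresses the change from admission to 6 hours on the admission value.

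**The concern.** The definition concerns the graft, whereas the measurement concerns the whole circulation. With a balloon or pump running, part of the recorded MAP is produced by the device. With ECMO or an RVAD, some blood also bypasses the right heart, so thermodilution need not give the graft's output. Section 7.7 has no rule for such a reading, so followed as written it enters as an ordinary value.

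These readings will not be spread evenly. Section 2 says mechanical support is used significantly less in patients without PGD, and device status is itself an input to the PGD definition. The doubtful values therefore gather in the group that CPOi is supposed to separate. A device started or stopped between the two readings also enters the 6-hour change as if the graft had altered. One aim of this feasibility trial is to learn whether CPOi is useful, and an uninterpretable value in the sickest recipients works against that aim.

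**Working it through.** The protocol gives no figure for CPOi to reproduce. The check has three parts.

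**1. Can the listed data identify an affected reading?** The CPOi readings fall at up to 1 hour and at 4 to 8 hours (6 ± 2) after ICU admission. Both lie inside the 24-hour PGD window.
- Balloon and pump both absent over 24 hours: neither reading was on support, so the recipient is clean.
- Either present: support may have covered the first reading, the second, both or neither. The listed variables do not distinguish these cases.
- The haemodynamic set kept for PGD does not help. Where several exist, section 7.7 keeps the one with the highest inotrope score, and lowest cardiac output on ties, so it need not coincide with either CPOi time.

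**2. How far could a reading move?** The protocol prints no formula. From its listed inputs I use

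index = CO × (MAP − CVP) / BSA.

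All values below are assumptions for illustration. BSA is 1.9 m² throughout and cancels in the ratios.

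| Situation | CO (L/min) | MAP (mmHg) | CVP (mmHg) | Index | Ratio |
|---|---|---|---|---|---|
| Failing graft, no device | 2.5 | 50 | 15 | 2.5 × 35 / 1.9 = 46.1 | 1.00 |
| Balloon adds 10 to MAP | 2.5 | 60 | 15 | 2.5 × 45 / 1.9 = 59.2 | 1.29 |
| Pump, same CO reading | 2.5 | 70 | 8 | 2.5 × 62 / 1.9 = 81.6 | 1.77 |
| Pump, low CO reading | 1.0 | 70 | 8 | 1.0 × 62 / 1.9 = 32.6 | 0.71 |

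The error can go either way. If the device starts between the readings, the same table gives apparent 6-hour changes of +13.2, +35.5 and −13.4 (from unrounded values), none of which measures recovery or decline of the graft's own power.

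**3. How many recipients?** Section 7.10 gives an estimated UK PGD rate of 36%, so 0.36 × 50 = 18 cases. The share on support at a CPOi reading is not in the protocol. Assuming 10% to 70% of those 18:
- 0.10 × 18 = 1.8, or 3.6% of 50
- 0.70 × 18 = 12.6, or 25.2% of 50

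**The case against.** The strongest reply is that the protocol is merely silent. It never instructs anyone to use readings taken on support, and handling them is ordinary material for an analysis plan, which is not at hand. That stands for the choice of analysis. It does not stand for the variable list: an analysis plan cannot condition on device status at two times if that status is not collected. The CRF is not shown either and may hold more than section 7.7 lists.

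Three further points stand in full. CPOi is labelled exploratory in section 3.3.3, and section 7.7 says its utility is to be judged on real-world data. Staff may take no thermodilution reading on ECMO; the value is then missing rather than distorted, although a device field would still help explain why. Section 10.8 offers queries for spurious data and robust estimators for outliers, but a supported reading can look normal and pass unnoticed.

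A reader might infer more than the documents support:
- *That affected values cannot be found at all.* The 24-hour flag confines them to recipients ever supported, so a sensitivity analysis without that group needs no new data.
- *That devices always make failing grafts look stronger and so shrink the contrasts.* The illustration runs both ways.
- *That the distortion is several-fold.* This needs thermodilution to read total flow. At an assumed 4.5 L/min the index is 4.5 × 62 / 1.9 = 146.8, a ratio of 3.19. Pump flow that bypasses the right heart would not be read that way, and section 2 names ECMO as the main type of support.
- *That the problem is one of severe PGD specifically.* The protocol does not print the severity grades.

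**Conclusion.** The point holds as a gap in data collection that leaves CPOi at odds with its own definition in recipients on support. Among recipients supported at any time in the first 24 hours, the listed data cannot show whether either CPOi reading reflects the graft alone, and nothing in the protocol keeps such readings out of the three planned uses. Size and direction are uncertain. The factors of 0.71 to 1.77 rest on assumed haemodynamics, and the 2 to 13 recipients of 50 rest on an assumed share of support and on support being confined to PGD cases. Readings taken before support starts or after it stops are not affected by this problem.

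The consequence is moderate. The primary feasibility endpoint and its success rule do not use CPOi. It still merits correction, because hypothesis 2 compares the solutions on CPOi and the trial summary lists it among the secondary outcomes.

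**What to change.** Add device status (none, IABP, ECMO, LVAD, RVAD, BiVAD) at each of the two CPOi reading times to the variable list in section 7.7. Then state how supported readings are handled:
- Do not treat a numeric CPOi measured on ECMO or a VAD as graft power. Flag readings taken on a balloon pump.
- For CPOi as a predictor of PGD, and for the 6-hour change, analyse off-device readings and report on-device readings separately. Do not rank on-device readings worst here: device status is an input to the PGD definition, so worst-ranking would build the association being tested into the predictor.
- For the comparison between solutions, a rank-based analysis with readings on ECMO or a VAD ranked worst may be given as a sensitivity analysis. It is useful because restricting to off-device readings conditions on something the solution may itself influence.

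The cost is two CRF fields taken from a record already being read, and fewer usable numeric CPOi values. The rank-based analysis gives no mean difference.

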 - c) Mixed or multiple ethnic groups
 - White and Black Caribbean
 - White and Black African
 - White and Asian
 - Any other Mixed or multiple ethnic background
 - d) White
 - English, Welsh, Scottish, Northern Irish or British
 - Irish
 - Gypsy or Irish Traveller
 - Roma
 - Any other White background
 - e) Other ethnic group
 - Arab
 - Any other ethnic group

The following baseline data will be recorded for eligible recipients who are approached but do not consent:

i. the reason for declining to take part (where given). This will take the form of free-text qualitative data, which will be analysed and grouped into categories for reporting by the trial steering committee.

The following baseline data will be collected for all eligible recipients who consent and receive a transplant:

- i. ABO blood group, a categorical variable with groups A, B, AB and O, reported as proportions.
- ii. Height, a continuous variable, measured in cm and reported as means.
- iii. Weight, a continuous variable, measured in kg and reported as means.

- iv. BMI (kg/m²), a continuous, calculated variable determined as weight in kg divided by height in metres, squared and reported as means.
- v. Pathology leading to need for transplant, a categorical variable with groups dilated cardiomyopathy, ischaemic cardiomyopathy, hypertrophic cardiomyopathy, restrictive cardiomyopathy, congenital heart disease, valvular heart disease and other, reported as proportions.
- vi. Transplant number, an ordinal variable with values, 1, 2, 3 or more, reported as proportions.
- vii. History of Hypertension, a categorical variable with categories yes/no, reported as proportions.
- viii. History of Diabetes mellitus, a categorical variable with categories yes/no, reported as proportions.
- ix. Renal function (eGFR and serum creatinine), continuous variables with serum creatinine at time of donation in milligrams per decilitre (mg/dL) and eGFR calculated using the Cockroft-Gault equation, reported as means.
- x. Liver function (bilirubin), a continuous variable measured on serum sample at the time of donation in milligrams per decilitre (mg/dL) and reported as means.
- xi. Infection from any source, treated with antibiotics, a categorical variable with categories yes/no, reported as proportions.
- xii. Left Ventricular Ejection Fraction, a continuous variable measured on the echocardiogram closest to the time of but prior to the transplant and given as a percentage, reported as means.

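### The body surface area formula takes height in metres with a constant that needs centimetres, so BSA comes out 28 times too small and CPOi 28 times too large.

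*Protocol*

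**What the plan says.** Section 7.7 states how CPOi is obtained: "CPOi is a calculated variable and will be obtained by uploading the following variables to the database". The variables listed are two thermodilution cardiac outputs (on arrival in ICU and about 6 hours later), BSA, mean arterial pressure and central venous pressure. The BSA item reads "Body surface area calculated using the DuBois and DuBois formula: Body Surface Area= 0.007184 x (Height(m"), with exponent 0.725 on height, followed by weight in kg with exponent 0.425.

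Section 3.3.3 describes cardiac power output as cardiac output times mean arterial pressure, "taking into account the filling state of the individual and indexed to body size". BSA is the only measure of body size among the listed inputs.

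Section 10.3.1 gives the unit for recipient height: "Height, a continuous variable, measured in cm and reported as means". The same section computes BMI from height in metres. No other part of the protocol corrects the BSA formula or gives a different constant for it.

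**The concern.** The constant and the height unit in the BSA formula cannot both be right, because together they give an adult BSA below 0.1 m². The formula is operative text: its result is one of the values from which CPOi is built.

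CPOi has a visible place in the plan. Section 3.2 names it in Hypothesis 2. The trial summary lists it among the secondary outcomes, although section 3.3.3 and the table in 3.3.4 class it as exploratory. Section 3.3.4 plans absolute differences between arms and between PGD groups. Section 10.5 plans a linear regression of the change in CPOi adjusted for its value at ICU admission.

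Two things are at stake. If everyone follows the text, CPOi is on the wrong scale. It could not be set against published values, such as those behind the rule-in, rule-out algorithm mentioned in 3.3.3, or used to plan the main trial. If some of the six centres use metres and others centimetres, values differ 28-fold between centres and the CPOi comparisons largely reflect the choice of unit.

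**Working it through.** The protocol prints no worked BSA or CPOi value, so there is no stated figure to reproduce. The printed formula can be evaluated directly.

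**Inputs from the protocol**
- Section 7.7: constant 0.007184; height in metres, exponent 0.725; weight in kg, exponent 0.425.
- Section 10.3.1: height recorded in cm, weight in kg.
- Section 3.3.3: power output is indexed to body size, so CPOi = CPO / BSA.

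**Assumed inputs:** the heights and weights below are illustrations. The protocol gives none.

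**Step 1: one adult, 175 cm and 80 kg**
- As printed: 0.007184 × 1.75^0.725 × 80^0.425 = 0.0694 m².
- With centimetres: 0.007184 × 175^0.725 × 80^0.425 = 1.956 m².

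**Step 2: the ratio**
- (100 × H)^0.725 / H^0.725 = 100^0.725 = 28.18. Height and weight cancel, so the factor is the same for every patient.

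**Step 3: a range of adult sizes**

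| Height, weight | BSA as printed (m²) | BSA with cm (m²) | Ratio |
|---|---|---|---|
| 150 cm, 45 kg | 0.049 | 1.37 | 28.18 |
| 160 cm, 60 kg | 0.058 | 1.62 | 28.18 |
| 175 cm, 75 kg | 0.068 | 1.90 | 28.18 |
| 180 cm, 80 kg | 0.071 | 2.00 | 28.18 |
| 195 cm, 120 kg | 0.089 | 2.51 | 28.18 |

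The metre column is impossible throughout, and the centimetre column is plausible throughout. The error therefore shows from the formula itself, without going back to its source.

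**Step 4: effect on CPOi**
- CPOi is inversely proportional to BSA, so CPOi as printed / CPOi with cm = 28.18. The unit conversion and the adjustment for filling state cancel in this ratio.
- The change from ICU admission to 6 hours is a difference of two CPOi values with the same BSA, so it is also inflated by 28.18.

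**Step 5: effect on the comparisons**
- *Metres used everywhere.* Every CPOi value is multiplied by one constant. Welch and rank tests, ratios, correlations, and the p-value of the treatment term in the section 10.5 regression are unchanged. Means, absolute differences and regression estimates are 28.18 times too large.
- *Mixed use.* As an illustration, suppose one of six equally recruiting centres uses metres and the true mean is the same in all six. The overall mean is then inflated by (5 × 1 + 1 × 28.18) / 6 = 5.53. That one centre supplies 28.18 / 33.18 = 85% of the total, so its patients dominate any comparison by arm or by PGD group.

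**Step 6: equivalent correction in metres**
- 0.007184 × 100^0.725 = 0.2025. Height in metres would need this constant.

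**The case against.** The case for treating this as minor is substantial.

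- **Standing of the endpoint.** Sections 3.3.3, 3.3.4 and 7.7 call CPOi exploratory. The primary feasibility endpoint does not use it. Cardiac index, recorded for PGD, is a separate variable that the protocol does not tie to this formula. This stands, and it limits the reach of the error, although the trial summary and Hypothesis 2 give CPOi more weight than the exploratory label suggests.
- **The error needs literal use.** The formula is named and height is recorded in centimetres, so entering the recorded height gives the right BSA. A value of 0.07 m² is also conspicuous, and section 10.8 provides for a call to the centre when spurious data are noticed at submission. This stands in part. Correct results would depend on staff departing from the text, and the protocol uses metres for BMI, so centimetres cannot be taken as always meant.
- **The data are recoverable.** Height, weight, cardiac output and pressures are all collected, so BSA and CPOi can be recomputed. This stands and is the main reason the point is not critical.
- **Comparisons fail only under mixed use.** This is correct. The protocol lists BSA among the uploaded variables without saying who calculates it, so mixed use is possible but not shown.
- **No external cut-off is planned.** Section 3.3.3 mentions the earlier algorithm only as previous work. This also stands. Even so, the absolute differences planned in 3.3.4 would be mis-scaled.

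**Conclusion.** The concern holds. As printed, the formula understates BSA and overstates CPOi by 100^0.725 = 28.18 in every patient. That factor is exact and rests only on the printed constant and exponent and on CPOi being divided by BSA.

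The practical effect depends on how sites apply the text. Use of centimetres despite the wording does no harm. Uniform use of metres corrupts absolute values and differences but not between-group tests. Mixed use corrupts the CPOi comparisons as well. The documents do not show which of these has happened.

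The consequences are confined to CPOi and are reversible from collected data. This is a correction the sponsor should make, but it does not threaten the trial's main conclusion.

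**What to change.** In section 7.7, change the height unit in the BSA formula from m to cm and keep the constant 0.007184. The alternative is to keep metres and print 0.2025, but centimetres match section 10.3.1.

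Two safeguards would help:
- State that BSA and CPOi are calculated centrally from height (cm), weight (kg), cardiac output, mean arterial pressure and central venous pressure, so that sites do not enter a locally computed BSA.
- Add a range check on BSA in the database. A window of 1.2 to 2.8 m² is a suggestion, not a figure from the protocol. It contains the 1.37 to 2.51 m² found above for the assumed range of adult sizes and would catch every metre-based value.

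If any BSA or CPOi values have already been entered, recompute them from the raw inputs. The cost is a one-word protocol correction and a check of the calculation wherever it is implemented. No new data are needed, and no treatment or clinical rule changes.
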